10.4 Measurement of Response

10.4.1 Although not required, it is encouraged that prostate tumor dimensions in centimeters or grams be recorded on the data collection forms for the follow up evaluations. PSA levels should be obtained per study calendar.

10.4.2 After study entry, disease evaluations will be made and recorded using the following criteria:

10.4.2.1 No Evidence of Disease (NED): No clinical evidence of disease on digital rectal examination and no PSA failure.

10.4.2.2 Equivocal Disease (ED): This rating will be assigned under the following circumstances:

- 1) If abnormalities are present on the prostate digital rectal examination but are thought to be abnormal due to treatment and felt not to represent tumor.
- 2) If clinical evidence of residual tumor is present but this has regressed from a previous examination (initial registration).
- 3) PSA 2.1 - 4 ng/mL. Rebiopsy is required, before starting hormone therapy, in any patient with PSA failure but with negative bone scan and CT scans. If the biopsy is negative, then they will be scored as NED.

10.4.2.3 Progressive Disease (PD): Progressive disease will be declared if one or more of the following criteria are met:

- 1) Clinical evidence in the prostate gland of disease progression or recurrence.
- 2) Clinical or radiographic evidence of tumor recurrence within the pelvic lymphatics or soft tissue beneath the bifurcation of the common iliac arteries,
- 3) Clinical or radiographic evidence of hematogenous (osseous, hepatic, etc.) and/or extrapelvic lymphatic or soft tissue relapse.

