10.5 Other Response Parameters

10.5.1 Disease-Free Interval: The disease-free interval will be measured from the date of accession to the date of documentation of progression or until the date of death (from other causes).

10.5.2 Time to Biochemical Failure: The RTOG-ASTRO definition (also known as the Phoenix definition) of PSA failure will be used. Thus, when the PSA rises by more than 2 ng/ml above the lowest level (nadir) achieved after treatment, biochemical failure has occurred and the date of the failure is recorded at the time the nadir plus 2 ng/ml level is reached.

10.5.3 Time to Local Progression: The time to progression will be measured from the date of study entry to the date of documented local progression as determined by clinical exam.

10.5.4 Time to Distant Failure: The time to distant failure will be measured from the date of study entry to the date of documented regional nodal recurrence or distant disease relapse. Patients with evidence of biochemical failure, but a negative prostate biopsy, will be considered as distant failure only.

10.5.5 Overall Survival: The survival time will be measured from the date of accession to the date of death. All patients will be followed for survival. Every effort should be made to document the cause of death.

10.5.6 Disease-Specific Survival Disease-specific survival will be measured from the date of study entry to the date of death due to prostate cancer. The following will be considered as failure events in assessing disease specific survival:

- Death certified as due to prostatic cancer.
- Death from other causes with active malignancy (clinical or biochemical progression).
- Death due to complications of treatment, irrespective of the status of malignancy.
- Death from other causes with previously documented relapse (either clinical or biochemical) but inactive at the time of death will not be considered in disease-specific survival, but will be analyzed separately.

10.5.7 Responsibilities of the Medical Monitor:

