APPENDIX III

AJCC STAGING SYSTEM PROSTATE, 6th Edition

DEFINITION OF TNM

Primary Tumor, Clinical (T)

TX	Primary tumor cannot be assessed
T0	No evidence of primary tumor
T1	Clinically inapparent tumor neither palpable or visible by imaging
	T1a Tumor incidental histologic finding in 5% or less of tissue resected
	T1b Tumor incidental histologic finding in more than 5% of tissue resected
	T1c Tumor identified by needle biopsy (e.g., because of elevated PSA)†
T2	Tumor confined with prostate*
	T2a Tumor involves one-half of one lobe or less
	T2b Tumor involves more than one-half of one lobe but not both lobes
	T2c Tumor involves both lobes
T3	Tumor extends through prostate capsule**
	T3a Extracapsular extension (unilateral or bilateral)
	T3b Tumor involves the seminal vesicle(s)
T4	Tumor is fixed or invades adjacent structures other than seminal vesicles: bladder neck, external sphincter, rectum, levator muscles and/or pelvic wall.

*Note: Tumor found in one or both lobes by needle biopsy, but not palpable or reliably visible by imaging, is classified as T1c

**Note: Invasion into the prostatic apex or into (but not beyond) the prostatic capsule is classified not as T3, but as T2.

Regional Lymph Nodes (N)

NX	Regional lymph nodes cannot be assessed
N0	No regional lymph node metastasis
N1	Metastasis in regional lymph node(s)

Primary Tumor, Pathologic (pT)

pT2*	Organ confined
	pT2a Unilateral, involving one-half of one lobe or less
	pT2b Unilateral, involving more than one-half of one lobe but not both lobes
	pT2c Bilateral disease
pT3	Extraprostatic extension
	pT3a Extraprostatic extension**
	pT3b Seminal vesicle invasion
	pT4 Invasion of bladder, rectum

*Note: There is no pathologic T1 classification

**Note: Positive surgical margin should be indicated by an R1 descriptor (residual microscopic disease).

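### A positive rebiopsy after PSA failure is not counted as local progression, because local progression is determined by clinical exam alone

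*Combined protocol and SAP*

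**What the plan says.** Local control is one of the phase II secondary objectives (2.4). Section 13.2.2 lists clinical progression, local/regional and distant, as a secondary endpoint, and 13.5.3 estimates local-regional and distant failure by cumulative incidence.

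The events are defined in sections 10.4 and 10.5:

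- Local progression (10.5.3) runs to the "date of documented local progression as determined by clinical exam".
- Progressive disease in the gland (10.4.2.3, criterion 1) is "Clinical evidence in the prostate gland of disease progression or recurrence".
- Distant failure (10.5.4) runs to the "date of documented regional nodal recurrence or distant disease relapse". The section adds: "Patients with evidence of biochemical failure, but a negative prostate biopsy, will be considered as distant failure only".
- The rebiopsy rule (10.4.2.2) reads: "Rebiopsy is required, before starting hormone therapy, in any patient with PSA failure but with negative bone scan and CT scans". It then gives a status to one of the two possible results: "If the biopsy is negative, then they will be scored as NED".
- Biochemical failure (10.5.2) is a PSA rise of more than 2 ng/ml above nadir, whatever the biopsy shows.

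**The concern.** The protocol requires the test that can show recurrence in the gland, but no endpoint definition uses a positive result. A negative rebiopsy has a stated consequence (distant failure under 10.5.4). A positive one has none.

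The patient concerned is foreseeable. T1 tumours are eligible, and Appendix III defines T1 as "Clinically inapparent tumor neither palpable or visible by imaging". An exam may well be normal in a man whose tumour could not be felt at entry. This argument rests mainly on T1c: T1a and T1b are defined by resected tissue while previous TURP is an exclusion, and T2a and T2b are also eligible.

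At stake is the local control estimate for a treatment that section 1.3 describes as strictly local. Any error from this gap runs one way, towards better local control. The disease-free interval (10.5.1) may be affected too, since it ends at documented progression.

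**Working it through.** **Step 1: apply the rules.** Take two men, each with PSA failure, negative bone scan and CT, and a normal exam. They differ only in the rebiopsy result.

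| Rule | Positive rebiopsy | Negative rebiopsy |
|---|---|---|
| 10.5.2 Biochemical failure | Yes | Yes |
| 10.5.3 Local progression | No: exam is normal | No: exam is normal |
| 10.5.4 Distant failure | No: no nodal or distant relapse, and the biopsy is not negative | Yes |
| 10.4.2.2 Status after rebiopsy | None stated | NED |
| 10.4.2.1 NED, which requires no PSA failure | Not met | Not met |
| 10.4.2.3 Criterion 1 | Not met, read literally | Not met |

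Sections 13.2.2 and 13.5.3 add no biopsy rule. The first man therefore stays event-free for both local and distant failure. The second man shows a related conflict: he is NED by 10.4.2.2, a distant failure by 10.5.4, and not NED by 10.4.2.1.

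**Step 2: size per man.** The plan gives no target, test or power for local control, so there is no figure to reproduce. Let k be the number of men with a positive rebiopsy whose exam stays normal, and N the number analysed. Section 13.3.2 gives 47 required and 50 accrued. The crude overstatement of local control is k/N:

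- k = 1: 1/47 = 2.1 points; 1/50 = 2.0 points
- k = 2: 2/47 = 4.3 points; 2/50 = 4.0 points
- k = 3: 3/47 = 6.4 points; 3/50 = 6.0 points

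This is the crude proportion. With incomplete follow-up, the cumulative incidence estimate of 13.5.3 would differ somewhat.

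**Step 3: an illustrative range.** The documents give neither the PSA-failure rate r nor the share s of those failures with a positive biopsy and a normal exam. Both are assumed here: r from 5% to 15%, s from 25% to 75%. Then k = N × r × s, and the overstatement is r × s. With N = 47:

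- Low: 47 × 0.05 × 0.25 = 0.59 men; 1.25 points
- Middle: 47 × 0.10 × 0.50 = 2.35 men; 5.0 points
- High: 47 × 0.15 × 0.75 = 5.29 men; 11.25 points

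The range shows only how the result depends on the two assumptions; it does not predict the number of such men in this trial.

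**The case against.** The best defence is that the intended rule can be inferred. Calling a negative biopsy a distant failure *only* makes sense chiefly if biopsy is what separates local from distant failure, so a positive one would be local. Scoring a negative result as NED likewise implies that a positive one is not NED. Criterion 1 also speaks of clinical evidence without naming the rectal exam, which 10.4.2.1 does name, so it could be read broadly.

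This stands as evidence of intent. It does not supply the rule. Section 10.5.3 names clinical exam and nothing else. Criteria 2 and 3 of progressive disease allow clinical or radiographic evidence, so the protocol names a further type of evidence where it wants one. Two readers could classify the same man differently.

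A second defence is that a purely clinical definition matches the endpoint as listed in 13.2.2 and may be deliberate. That is possible. If so, the plan should say that biopsy-proven recurrence with a normal exam does not count, so that the local control figure can be read correctly.

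Third, the impact is limited. Local control is one of several secondary estimates without a decision rule, and the man in question still counts as a biochemical failure. This stands.

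**Conclusion.** The gap is real on the text. A man with PSA failure, negative scans, a normal exam and a positive required rebiopsy is left out of local failure when the definitions are applied literally, and local control is overstated by about 2 points for each such man. The number of such men is unknown and may be zero. The conclusion assumes the literal reading of 10.5.3 and an exam that stays normal up to the analysis. The primary late-toxicity endpoint, the sample size and the biochemical result do not depend on it.

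A reader might infer two stronger claims that the documents do not support:

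- *That failures are moved from local to distant.* They are not. Men with a positive rebiopsy drop out of both counts. The distant failures created by 10.5.4 are the men with a negative rebiopsy, and counting positive biopsies as local would not change their number.
- *That local failure would be 0% as written.* This would hold only if no man had local failure detected by exam, at the time or later. Exam-detected local failures are still counted.

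**What to change.** In 10.5.3 and in criterion 1 of 10.4.2.3, define local progression as clinical evidence of progression or recurrence in the gland, or a post-treatment biopsy positive for prostate adenocarcinoma in a man with PSA failure. Fix one event date, either the biopsy date or the PSA-failure date, and carry the definition into the local-regional failure estimate of 13.5.3.

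In the same edit, reconcile 10.4.2.1, 10.4.2.2 and 10.5.4 so that the man with PSA failure and a negative biopsy has one status.

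The cost is wording. The biopsy is already required, so no procedure is added and treatment does not change. The local control figure may become slightly less favourable.

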11.1 Summary of Data Submission

Item	Due
Demographics	Within 2 weeks of study entry
Eligibility and Entry Characteristics including baseline H&P and PSA	Within 2 weeks of study entry
Pathology Report	Within 2 weeks of study entry
AUA and EPIC baseline forms	Within 2 weeks of study entry
SBRT dosimetry information	Within 1 week after completion of SBRT
Follow-up H&P data including PSA	After last SBRT treatment, post SBRT follow-up at 1.5, 3, 6, 9, 12 months, then every 6 months to 3 years; then annually for years 3-10

AUA and EPIC post treatment forms

After last SBRT treatment, post SBRT follow-up at 1.5, 3, 12, and 18 months

Adverse Event assessment

After each SBRT treatment, then post SBRT follow-up at 1.5, 3, 6, 9, and 12 months, then every 6 months to 3 years; then annually for years 3-10

13.0 STATISTICAL CONSIDERATIONS

13.1 Phase I Study Endpoints

13.1.1 Primary Endpoint

The primary endpoint of the phase I portion is to either reach the maximum tolerated dose (MTD) or a dose of 50 Gy total (whichever comes first) by escalating the dose of SBRT toward the tumocidal dose of 50 Gy total. Patients will be treated in cohorts of seven to fifteen,.. Toxicity will be graded using the NCI Common Toxicity Criteria for Adverse Events (CTCAE) v. 3.0. A dose- limiting toxicity (DLT) is any treatment-related grade 3, 4, or 5 toxicity in the following categories (specific conditions listed in section 6.9): gastrointestinal, renal, genito-urinary, sexual- reproductive, or neurological. A DLT will also include any treatment-related grade 4 or 5 toxicity related in the following categories (specific conditions listed in section 6.9): constitutional symptoms. In addition, any other grade 4 or 5 toxicity attributed to the therapy constitutes DLT. All reported DLTs will be verified by study chair, data monitoring committee, and independent review before final determination that a DLT has in fact occurred. Doses will be escalated an additional 0.5 Gy per treatment for 5 treatments (total 2.5 Gy per increment). The phase I portion of the study will be completed when either of the following events occur: 1) the MTD for a cohort is reached or 2) when the highest protocol dose level is treated and tolerated (10 Gy per fraction, total 50 Gy) where we consider the therapy likely to be tumocidal per determination of the investigators.

13.1.2 Phase I Dose Escalation

The phase I study is designed to end if the rate of DLTs within 90 days from the start of treatment is 33% or higher. For each dose level cohorts, a total of seven to fifteen patients will be enrolled. If zero out of the first seven with 90 day follow-up, two or fewer out of the first nine with 90 day follow-up, three or fewer out of the first twelve with 90 day follow-up, or four or fewer out of the first fifteen of patients with 90 day follow-up experience a DLT as defined above, then the dose will escalate to the next dose level. If three or more of the first nine patients, four or more of the first twelve, or five or more of the first fifteen patients experience a DLT, then the MTD will be considered to have been exceeded. The MTD will be defined as the immediately previous lower dose level tolerated. The probability that at least two of nine patients will experience a DLT when the true rate of acute DLTs is 33% is 0.80; that is, the probability of making the correct decision if the true DLT rate is at least 33% is 0.80.

The sample size of the phase I component of this study will not exceed 45 patients.

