13.1.3 Phase I Waiting Periods

Dose escalation on the phase I portion of this study should not occur until a sufficient waiting period has occurred after patients have been treated. A period of 90 days must pass in order to assess toxicity. If 90 days have transpired without DLT in each

of the first seven (7) patients enrolled to a specific dose level, then dose escalation to the next level may proceed. Patients will continue to be enrolled to each dose level (up to a maximum of 15 patients) with ongoing assessment of those reaching 90 day follow-up so long as either criteria for defining the MTD (section 13.1.2) or criteria for further dose escalation is not reached. If fifteen patients are enrolled to a given dose level yet criteria for adequate follow-up are not reached in a representative sample of patients (section 13.1.2), further enrollment to the protocol will be suspended until adequate follow-up is reached.

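### The 0.80 given in phase I as the chance of a correct decision belongs to the wrong event and is miscalculated; the written rule gives 0.61 to 0.62, and its 9-, 12- and 15-patient criteria do not fit together

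*Combined protocol and SAP*

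**What the plan says.** Section 13.1.2 (Phase I Dose Escalation) sets the target: phase I is "designed to end if the rate of DLTs within 90 days from the start of treatment is 33% or higher". On cohort size it says: "For each dose level cohorts, a total of seven to fifteen patients will be enrolled".

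The dose goes up on any of four results. For the two smaller cohort sizes the condition reads: "If zero out of the first seven with 90 day follow-up, two or fewer out of the first nine with 90 day follow-up". For the two larger sizes the wording is: "three or fewer out of the first twelve with 90 day follow-up, or four or fewer out of the first fifteen of patients". The MTD is taken to be exceeded on the complementary counts: "If three or more of the first nine patients, four or more of the first twelve"; at fifteen patients the corresponding count is five.

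The section then gives its only operating characteristic: "The probability that at least two of nine patients will experience a DLT when the true rate of acute DLTs is 33% is 0.80". It restates this as the probability of deciding correctly when the true DLT rate is at least 33%.

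Section 13.1.3 (Phase I Waiting Periods) allows accrual at a dose level to continue, up to 15 patients, "so long as either criteria for defining the MTD (section 13.1.2) or criteria for further dose escalation is not reached".

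**The concern.** At a true DLT rate of 33%, the correct decision is to declare the MTD exceeded. Under the written rule that takes three DLTs in nine, yet the probability sentence starts counting at two. Exactly two of nine is an escalation result ("two or fewer out of the first nine with 90 day follow-up"), so the sentence credits a wrong decision as a right one. The value 0.80 also looks too low for the event named.

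A second problem lies in the rule itself. At nine patients, two or fewer and three or more leave no undecided result, so it is unclear what the criteria at 12 and 15 are for.

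This is the only figure the protocol offers on how well phase I protects patients from too high a dose. DLTs here include treatment-related grade 3 to 5 gastrointestinal, renal, genitourinary, sexual-reproductive and neurological events (section 13.1.1). The selected dose is carried into phase II (section 13.2), and phase I patients treated at that dose count in the phase II analysis (section 13.3.2).

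**Working it through.** **Inputs.** All come from section 13.1.2: DLT rate p = 0.33 (1/3 also tried, since 33% may be rounded); escalate at 0/7, ≤2/9, ≤3/12 or ≤4/15; exceeded at ≥3/9, ≥4/12 or ≥5/15; stated probability 0.80 for ≥2/9. DLTs are treated as independent, so the count X in nine patients is Binomial(9, p).

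**1. The plan's own figure.** P(X ≥ 2) = 1 − P(0) − P(1).
- p = 0.33: P(0) = 0.67⁹ = 0.0272 and P(1) = 9 × 0.33 × 0.67⁸ = 0.1206, so P(X ≥ 2) = 0.852.
- p = 1/3: P(X ≥ 2) = 0.857.

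The stated 0.80 is 5 to 6 percentage points below this. Values near 0.80 do arise for at least two DLTs under settings that the protocol does not state:

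| Setting | P(at least 2) |
|---|---|
| 8 patients, 33% or 1/3 | 0.799 to 0.805 |
| 9 patients, 30% | 0.804 |
| Poisson approximation, mean 9p | 0.796 to 0.801 |

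The source of 0.80 is therefore unknown. The Poisson approximation is poor at n = 9 and p = 0.33.

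**2. The event that stops the dose.** P(X ≥ 3) = P(X ≥ 2) − P(2).
- p = 0.33: P(2) = 36 × 0.33² × 0.67⁷ = 0.2376, so P(X ≥ 3) = 0.8522 − 0.2376 = 0.615.
- p = 1/3: P(X ≥ 3) = 0.623.

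The early escalation at 0/7 changes nothing, because a cohort with 0/7 can have at most 2/9. The chance of escalating past, or accepting, the dose is 1 − 0.615 = 0.385 (0.377 at 1/3). The implied chance is 1 − 0.80 = 0.20.

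| True DLT rate | P(≥3 of 9) |
|---|---|
| 25% | 0.40 |
| 33% to 1/3 | 0.61 to 0.62 |
| 40% | 0.77 |
| about 42% | 0.80 |

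**3. Most favourable reading of the stopping rule.** Suppose accrual always runs to 15 and a crossing at 9, 12 or 15 stops the dose, whatever the escalation criteria say at 9 and 12. P(exceeded) is then 0.712 to 0.721 if 0/7 is still final, and 0.718 to 0.727 if it is not. Taken singly, P(≥4 of 12) is 0.597 to 0.607 and P(≥5 of 15) is 0.585 to 0.596. None of these reaches 0.80.

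**4. Consistency of the 9-, 12- and 15-patient criteria.** At nine evaluated patients, ≤2 escalates and ≥3 stops, and these cover every result. Applied in sequence, the probability of reaching the 12-patient criterion is zero.

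If patients beyond the ninth are already treated and are counted, decisions can reverse:
- 2/9 (escalate), then 2 of the next 3, gives 4/12 (exceeded).
- 3/9 (exceeded), then 0 of the next 3, gives 3/12 (escalate).

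At p = 0.33, for a cohort of 15 in full:
- P(≤2/9, then ≥4/12) = 0.065.
- P(≤2/9 and ≤3/12, then ≥5/15) = 0.039.
- The total is 0.103 before rounding, so about 10% of such cohorts satisfy both an escalate criterion and an exceeded criterion.

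**The case against.** The best defence concerns scope. The escalation criteria ask for 90-day follow-up, while the exceeded criteria carry no such condition, and section 13.1.3 lets accrual continue while follow-up matures. Patients 10 to 12 may therefore be on treatment before the nine-patient escalation criterion can be met, and four DLTs in the first twelve could act as an early safety stop. On that reading the larger-cohort stopping boundaries can be reached, and the chance of passing a dose with a 33% DLT rate is nearer 28% than 38%. The 10% overlap applies only to cohorts that fill to 15; the protocol gives no phase I accrual rate, so its overall frequency is unknown. In addition, 33% is the least favourable point of the range the sentence covers, nothing in the plan visibly derives a sample size from the 0.80, DLTs are independently verified, and phase II has its own toxicity boundaries in section 14.2.

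Much of this stands. The larger criteria are unreachable only if the nine-patient criteria are applied in sequence to complete follow-up, and 38% belongs to the nine-patient rule alone. But none of it yields 0.80. The protocol makes its claim at 33%, so that is the rate at which to check it. The phase II boundaries limit the harm from too high a dose; they do not correct the phase I figure. The early-stop reading is also the one under which a cohort can meet two opposite criteria, and the protocol does not say which prevails.

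**Conclusion.** The concern holds. The probability sentence uses an event that does not match the rule, and its value is wrong for that event under an exact binomial calculation (0.852 to 0.857). For the nine-patient rule as written, the chance of stopping at a 33% DLT rate is 0.61 to 0.62. The chance of a wrong decision is about 38%, nearly twice the implied 20%. If crossings at 12 and 15 also count, the stopping chance is 0.71 to 0.73 and the wrong-decision risk 27% to 29%. Reading two as a slip for three does not rescue 0.80; it moves the true value further away.

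Separately, the 12- and 15-patient criteria are redundant once nine patients are fully evaluated, and can conflict with the nine-patient decision when accrual has run ahead.

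These results assume independent DLTs with a common rate. The 10% overlap further assumes that all 15 patients are enrolled and evaluated. This should be corrected: a safety claim in the protocol is false under its own rule, and some outcomes point to opposite decisions.

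**What to change.** In section 13.1.2:

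1. Decide whether the stopping threshold at nine patients is two or three DLTs, and make the rule and the probability sentence agree. The threshold itself is a clinical choice on which this review takes no position.
2. Replace 0.80 with the probability for the rule kept: 0.61 to 0.62 for three or more of nine, or 0.85 to 0.86 for two or more of nine. If boundaries at 12 and 15 are to operate, recompute for the whole scheme.
3. State the resulting chance of escalating past, or accepting, a dose whose true DLT rate is 33%.
4. Rewrite the criteria so that every result at 9, 12 and 15 patients leads to one decision. Either drop the 12- and 15-patient criteria, or leave an undecided zone at nine and twelve that sends the cohort on. Say which decision prevails when later patients are already treated, and align section 13.1.3.

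The cost is revised wording and recomputed probabilities, with no extra patients required. If the three-of-nine rule stays, the stated protection will look weaker than it does now.
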